7.4.1 Medical History

Medical history will be coded using the Medical Dictionary for Regulatory Activities (MedDRA) Version 23.1 (or a later version if updated during the study). All medical history will be listed, and the number and percentage of subjects with any medical history will be summarized for the ITT population by system organ class (SOC) and preferred term (PT) for each treatment group and overall.

7.4.2 Previous and Concomitant Medications

Medications received prior to or concomitantly with study drug will be coded by Covance using the WHODrug Dictionary Version March 2019 Global Dictionary Version B3 (or a later version if updated during the study), Anatomical Therapeutic Chemical (ATC) Classification codes.

Prior medications and concomitant medications are defined as follows:

Prior medications are those taken prior to study drug with a stop date prior to the first dose of study drug.

Statistical Analysis Plan

Sponsor Name: Clear Creek Bio, Inc.
Sponsor Protocol ID: CCB-CRISIS-02

Covance Study ID: 000000207395

Concomitant medications are those with a start date on or after the first dose date of study drug, or those with a start date before the first dose date of study drug and a stop date on or after the first dose date of study drug or ongoing end of study.

If a medication cannot be classified as "prior" or "concomitant" after applying imputation rules for missing/incomplete dates, it will be classified as concomitant.

Prior medications and concomitant medications will be listed together and summarized separately for the ITT population.

The number and percentage of subjects using each medication will be displayed together with the number and percentage of subjects using at least one medication within each therapeutic class (ATC-Level 2), chemical subgroup (ATC-Level 4), and generic term.

7.5 Measurements of Study Drug Compliance

Percentage compliance is calculated as:

100 * actual number of capsules taken/expected number of capsules taken, where expected capsules taken is specified to be 5.

Percentage compliance will be summarized descriptively by treatment group for the Safety population.

The number and percentage of compliant subjects will be presented for the Safety population, where compliant is defined as percentage compliance between 80.0% and 100.0% inclusive. The number and percentage of subjects with compliance <80.0% as well as number and percentage of subjects who received more than one capsule in a calendar day will also be presented.

7.6 Efficacy

7.6.1 Primary Efficacy Analysis

SARS-CoV-2 Viral load will be reported as below.

- # of copies/mL;
- <# of copies/mL, if detected but under the lower limit of quantification (LLOQ);
- no SARS CoV-2 detected, if not detected.

SARS-CoV-2 Viral load (\log_{10} copies/mL) and change from baseline will be summarized by visit using standard descriptive statistics for the MES population. The baseline value is defined as last scheduled or unscheduled viral load collected prior to the first dose of study drug. For post-baseline, only data from scheduled visits will be included in the summary tables. For the analysis purpose, viral load below the

Statistical Analysis Plan

Sponsor Name: Clear Creek Bio, Inc.
Sponsor Protocol ID: CCB-CRISIS-02

Covance Study ID: 000000207395

LLOQ will be considered equal to the LLOQ. Number of subjects with undetectable SARS-CoV-2 viral load at each visit will be presented as well.

Changes from baseline in SARS-CoV-2 viral load data (\log_{10} copies/mL) will be statistically analyzed using a mixed model for repeated measures (MMRM) in the MES population. The model will contain baseline as a covariate, treatment, day and treatment-by-day interaction as fixed effects. The unstructured covariance matrix will be selected initially; if this analysis fails to converge another covariance structure will be selected based on AIC and BIC values. The least square (LS) means and treatment difference at Days 4, 8, 12, 15, 22 and 29 will be calculated and presented with their corresponding 95% confidence intervals (CIs). All available data will be used in the analysis.

7.6.2 Secondary Efficacy Analysis

The duration of viral shedding is defined as the time (in days) from Day 1 to the first time where no SARS-CoV-2 is detected. When deriving viral shedding, any missing viral load data will be considered detectable. Subjects will be censored at the last SARS-CoV-2 viral load test if SARS-CoV-2 is detected at all tests.

Kaplan-Meier curves will be used to estimate the distribution of duration of viral shedding in the MES population. The 50th percentile of Kaplan-Meier estimates will be used to estimate the median duration of viral shedding. A two-sided 95% CI will be provided for this estimate. The 25th and 75th percentiles, and the range (minimum, maximum) will be presented as well. The range will be determined including censored observations. Duration of viral shedding will be compared between treatment groups using a unstratified log rank test. The two-sided p-value for the log rank test will be presented.

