6.2 Secondary Endpoints

The secondary endpoints of this study are:

Through Day 29:

- Rates of AEs and SAEs including laboratory assessments;
- Duration of viral shedding;
- Percentage of subjects requiring admission as an inpatient for >24 hours.
- All-cause mortality.

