As much of the study as possible will be conducted via telemedicine remote from the site (e.g., consent, medical history, concomitant medications may be collected remotely). Subjects will be visited at home (or place of residence) by a home health nurse or come to the site for an in-person visit at Screening and on study Day 1. The subjects will be visited at home for Study Days 8, 15, and 29. On study Days 4, 12, and 22 the vital signs and saliva collections will be observed via telemedicine by the study site staff. Site staff will have a telephone call with subjects on study days 2, 3, 5, 6, and 7 to assess changes in concomitant medications and to assess adverse events, especially those that may indicate thrombocytopenia, e.g., unusual bruising, epistaxis, gingival bleeding, etc., and mucositis. Subjects will be provided with a pulse oximeter and thermometer during the Screening or Day 1 visit, as well as being trained on the use of these devices during the visit. Training will also be provided for the saliva collection required for viral load testing. Assessments will be recorded by the study staff during home and clinic visits and by the site staff during telemedicine visits. These data will be entered in the eCRF by the site staff or as determined by the study team.

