7.6.3 Exploratory Efficacy Analysis

7.6.3.1 Time to Viral Clearance

The time to viral clearance is defined as the time (in days) from Day 1 to the first time where no SARS-CoV-2 is detected for subjects with two consecutive tests of undetectable SARS-CoV-2. When deriving viral clearance, any missing viral load data will be considered detectable. Subjects without two consecutive tests of undetectable SARS-CoV-2 will be censored at the last SARS-CoV-2 viral load test.

Time to viral clearance will be analyzed using the same method as specified in section 7.6.2 for the secondary efficacy endpoint in the MES population.

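### SAP 7.6.3.1, read literally, dates viral clearance at an isolated early negative, the same date as SAP 7.6.2, which disregards later detectable results

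*SAP*

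**What the plan says.** The protocol (v5.0, 6.2) lists "Duration of viral shedding" as a secondary endpoint without defining it. Section 6.3 lists time to viral clearance as exploratory and attaches the two-negatives requirement to that endpoint only.

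SAP 7.6.2 measures shedding "from Day 1 to the first time where no SARS-CoV-2 is detected". It adds that "any missing viral load data will be considered detectable" and "Subjects will be censored at the last SARS-CoV-2 viral load test if SARS-CoV-2 is detected at all tests". The comparison uses Kaplan-Meier curves and an unstratified log-rank test in the Microbiology Evaluable Set (MES).

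SAP 7.6.3.1 defines time to viral clearance as "from Day 1 to the first time where no SARS-CoV-2 is detected for subjects with two consecutive tests of undetectable SARS-CoV-2". Missing tests again count as detectable, and a subject who never has two in a row is censored at the last test. The method is that of 7.6.2.

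Under SAP 7.6.1, a result that is detected but below the quantification limit is reported separately from a result with no virus detected. Only complete non-detection can therefore end shedding.

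**The concern.** There are two separate issues.

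**Clearance (7.6.3.1).** The two-in-a-row requirement decides who has an event, but the date is still the first undetectable test of any kind. If that test was isolated and virus was detected afterwards, clearance is dated before the virus had cleared. A programmer following the text would use that date, and one following the likely intention would use the first test of the pair. The confirmation requirement then protects the event indicator but not the event time.

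**Shedding (7.6.2).** One undetectable saliva test ends shedding for good, whatever follows. If isolated negatives occur throughout shedding, slower clearers have more tests at which one can occur. Their recorded times are shortened more, and the difference between arms shrinks. The secondary objective is a shorter duration of shedding, and the trial is meant to inform later study design, so a diluted comparison could mislead that planning.

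**Working it through.** **Inputs.** Protocol 9.4 gives six post-baseline tests: Days 4, 8, 12, 15, 22 and 29. Code each as U (no virus detected) or D (detected, including below the quantification limit, or missing). The plan states no power, event count or effect size for this endpoint, so there is no figure to reproduce.

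**Step 1: apply the rules.**

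| Pattern, Days 4-8-12-15-22-29 | 7.6.2 | 7.6.3.1 read literally | First test of first pair |
|---|---|---|---|
| D-D-U-U-U-U | Day 12 | Day 12 | Day 12 |
| U-D-D-U-U-U | Day 4 | Day 4 | Day 15 |
| U-D-D-D-D-D | Day 4 | censored Day 29 | censored Day 29 |
| U-U-D-D-U-U | Day 4 | Day 4 | Day 4 |

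**Step 2: count the patterns.** There are 2^6 = 64.

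- At least one U: 64 − 1 = 63. Section 7.6.2 records an event in all of them.
- A D somewhere after a U: the 7 patterns of the form D…D U…U have none, so 64 − 7 = 57.
- No two U in a row: the counts for lengths 1 to 6 are 2, 3, 5, 8, 13, 21. So 64 − 21 = 43 patterns contain a pair. In all 43 the literal 7.6.3.1 date equals the 7.6.2 date.
- One or more U but no pair: 21 − 1 = 20. Section 7.6.2 counts an event and 7.6.3.1 censors.
- An isolated first U, then a later pair: first U on Day 4, D on Day 8, pair among the last four tests, 16 − 8 = 8; first U on Day 8, D on Day 12, pair among the last three, 8 − 5 = 3; first U on Day 12, D on Day 15, then U-U, 1. Total 8 + 3 + 1 = 12 of the 43.

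These are counts of patterns, not probabilities.

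**Step 3: possible size. Every input is assumed.** If each test during shedding has chance f of an isolated negative, the chance of at least one in three tests is 1 − (1 − f)^3: 14% at f = 5%, 27% at 10%, 49% at 20%.

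Simulated log-rank power (two-sided 5%, 10,000 trials) assumes Weibull clearance times of shape 2, medians of 14 and 9.5 days (hazard ratio (14/9.5)^2 ≈ 2.2), 50 per arm and complete data:

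| Isolated negatives | 7.6.2 | 7.6.3.1 literal | First of pair |
|---|---|---|---|
| None | 95% | 94% | 94% |
| 5%, constant | 86% | 91% | 94% |
| 10%, constant | 72% | 86% | 92% |
| 20%, constant | 45% | 72% | 87% |
| 30% at clearance, fading earlier | 92% | 92% | 93% |
| 10%, last 4 days only | 94% | 94% | 94% |
| 20%, last 4 days only | 94% | 93% | 93% |

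A separate run with shape 1.5 and medians of 14 and 9 days shows the same pattern: 86%, 84% and 84% with no isolated negatives, and 60%, 78% and 83% at 10% constant.

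At 10% constant misses in the first setting, 18% of placebo and 10% of brequinar subjects have a detectable result after their recorded end of shedding. The Day 15 difference in the share no longer shedding is 88.3 − 70.2 = 18.1 points under 7.6.2, 84.1 − 58.6 = 25.5 under pair dating, and 82.2 − 54.7 = 27.5 in truth. With 10% late-only misses, 0.4% of subjects have a later detectable result and there is no dilution.

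**The case against.** The strongest reply is that 7.6.2 is not defective. It is a complete first-event rule: every pattern gets exactly one date or a censoring time. The protocol ties two negatives to clearance and not to shedding, so the SAP follows a deliberate split. This stands.

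It can also be said that 7.6.3.1 surely means the first test of the pair. Probably so, but the text does not say it, and the literal date differs in 12 of 43 patterns. This supports a one-clause fix, not leaving the wording alone.

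The plan also has safeguards. Detection below the quantification limit still counts as detected. Protocol 9.4 adds that "On study Days 4, 12, and 22 the vital signs and saliva collections will be observed via telemedicine by the study site staff". SAP 7.6.1 promises that "Number of subjects with undetectable SARS-CoV-2 viral load at each visit will be presented as well", and the listings would show a rebound. These narrow the problem and make it visible, but they do not change the Kaplan-Meier estimate or the log-rank test.

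A reader might infer that 7.6.2 should be replaced by a pair rule, or merged with clearance. The documents do not support that. The gain depends on isolated negatives being spread through shedding, and no document says they are. Because a missing test counts as detectable, one lost sample breaks a pair. With 10% of tests missing (same assumed setting), 7.6.2 against the pair rule gives 94% against 86% with no isolated negatives, 94% against 87% with late ones, 84% against 84% at 5% constant and 70% against 82% at 10% constant. The better rule turns on two unknown rates, and the secondary endpoint would become the exploratory one.

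**Conclusion.** The clearance date in 7.6.3.1 is wrong as written for any subject whose first undetectable test is isolated and who later has two in a row. This follows from the text and needs no assumption. For subjects with a pair, the literal clearance date never differs from the shedding date, so as written the exploratory analysis is only a partial check on the secondary one.

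For 7.6.2 the conclusion is conditional. The rule dilutes the arm difference if isolated negatives are spread through shedding, and does not if they occur only near clearance. The size is unknown: miss rate, missing-test rate and effect size are all absent from the documents. The simulated powers also assume 50 per arm, whereas the analysis set is the MES, which may be smaller.

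Two further inferences are not supported. The false-positive rate is not inflated: simulated at 5.3%, 5.0% and 5.4% for 0, 10 and 20% constant misses. Nor is duration always understated, because visits are 3 to 7 days apart: the assumed placebo mean is off by +2.5, +0.9, −0.5 and −3.0 days at 0, 5, 10 and 20%.

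Severity is minor. Protocol section 11 makes all testing exploratory and descriptive, and the primary repeated-measures model is unaffected.

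**What to change.** 1. **SAP 7.6.3.1:** state that the clearance date is the date of the first test in the first pair of consecutive undetectable tests. Leave the censoring rule unchanged.
2. **SAP 7.6.2:** keep the definition and add that detectable results after the first undetectable test are disregarded.
3. **SAP 7.6.2:** report by arm the number of subjects with a detectable result after their recorded end of shedding. Count observed detections only, not missing tests treated as detectable. This shows from the trial's own data whether dilution is a live issue.
4. Name the corrected 7.6.3.1 analysis as the confirmed-negative sensitivity analysis for shedding.

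**Cost:** a few sentences, one extra table row and a little programming; no new visits or samples. In the pair-based analysis Day 29 can only confirm, so the latest possible event date is Day 22. The two-in-a-row condition already implies that limit. Rebound after two negatives (U-U-D-D-U-U) is still dated Day 4. The changes should be made before unblinding; the protocol allows the SAP to be finalized up to database lock.

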7.6.3 Exploratory Efficacy Analysis

7.6.3.1 Time to Viral Clearance

The time to viral clearance is defined as the time (in days) from Day 1 to the first time where no SARS-CoV-2 is detected for subjects with two consecutive tests of undetectable SARS-CoV-2. When deriving viral clearance, any missing viral load data will be considered detectable. Subjects without two consecutive tests of undetectable SARS-CoV-2 will be censored at the last SARS-CoV-2 viral load test.

Time to viral clearance will be analyzed using the same method as specified in section 7.6.2 for the secondary efficacy endpoint in the MES population.

7.6.3.2 Viral Culture

Viral culture will be listed and summarized by treatment group and visit.

Viral culture data and changes from baseline in viral culture will be summarized by visit using standard descriptive statistics for the MES population. The baseline value

Statistical Analysis Plan

Sponsor Name: Clear Creek Bio, Inc.
Sponsor Protocol ID: CCB-CRISIS-02

Covance Study ID: 000000207395

is defined as last scheduled or unscheduled value collected prior to the first dose of study drug. For post-baseline, only data from scheduled visits will be included in the summary table.

7.6.4 Secondary Clinical Analysis

7.6.4.1 Hospital Admission

Subjects requiring hospital admission as an inpatient for >24 hours will be analyzed in the ITT population. Number and proportion of subjects requiring hospital admission along with 95% exact binomial CI (Clopper-Pearson) will be presented for each treatment group. Two-sided 95% CI will also be presented for the difference in percent of subjects requiring hospital admission between treatment groups with an approximate normal distribution. The Fisher's exact test will be used to compare the proportion of subjects requiring hospital admission. The two-sided p-value for the Fisher's exact test will be presented.

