Design	
This will be a phase 2 randomized, double blind, multi-center study with approximately 100 subjects. All subjects will receive SOC per relevant guidelines for treatment of out-patients with COVID-19 infection. In addition to SOC, subjects will self-administer one capsule once daily for 5 days.
 
To be eligible for screening, subjects must have a documented positive SARS-CoV-2 test result and have at least one symptom consistent with SARS-CoV-2 infection in the opinion of the investigator. Subjects will have a Screening Visit followed as soon as possible with randomization on Study Day 1. First dose of study drug must take place \leq 7 days from onset of first symptom. Study procedures are presented in detail in the Schedule of Events. Study visits (virtual or in person) will take place at Screening and on Study Days 1 - 8, 12, 15, 22, and 29. The visits that include bloodwork must be conducted at the study site or arrangements made for sample collection at the subject's home or other appropriate location. Other visits/visit activities for that visit may be conducted remotely using telephone, telemedicine or other remote technique. Subjects are to self-collect a viral load sample, obtain their respiratory rate, heart rate, body temperature and SpO₂, and complete a symptom assessment with the site via telemedicine on Days 1, 4, 8, 12, 15, 22, and 29. The site will also have a telephone call with the subject on Study Days 2, 3, 5, 6, and 7 for changes in concomitant medications and assessment of adverse events, especially those that may indicate thrombocytopenia and mucositis. Screening and study Day 1 are to be conducted at the site unless the site is unable to accommodate in-person visits. If the site is unable to accommodate in-person visits, a home visit may be arranged as long as first dose can be achieved within 7 days of symptom onset. Days 8, 15, and 29 require in-person visits and will be conducted via home visit. Any in-person visit may also have telemedicine or telephone components if all study activities cannot be completed in person. Telemedicine only visits will be conducted by site staff on study Days 4, 12, and 22.

Sample Size:	Approximately 100 subjects will be randomized to 5 days of either SOC + brequinar 100 mg or SOC + placebo in a 1:1 ratio (approximately 50 subjects assigned to brequinar 100 mg and 50 subjects to placebo).
Number of Sites:	Approximately 15
Study Period:	An enrollment period of 3 months is expected.

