2.4 Randomization

The trial will be conducted in double blinded, randomized manner with random assignment to standard of care plus brequinar or standard of care plus placebo in a 1:1 ratio at each site. The brequinar and placebo capsules will be provided to each participating institution in pre-numbered bottles intended for individual subjects to be dispensed by the institution's pharmacist or designated person. Randomization assignments will be provided by an independent statistician at Prosoft Clinical to the drug packaging company. The pharmacist/designated person will dispense the next number in sequence to the next patient who qualifies for the study at an individual site.

3. Efficacy and Safety Variables

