7.1 General Principles

All data processing, summarization and analyses will be performed using Covance's SAS Environment / Version 9.3 (or later) of the SAS® statistical software package.

The following principles will be applied to all tables, figures, and listings (TFLs) unless otherwise stated:

Principle	Value
Significant tests	Two-sided and use a 5% significance.
Treatment group labels and order presented	SOC + Brequinar 100 mg SOC + Placebo
Tables	Data in summary tables presented by treatment group, assessment and visit (where applicable), unless otherwise specified.
Listings	All data collected presented by treatment group, site, subject, assessment and visit (where applicable), unless otherwise specified.
Descriptive summary statistics for continuous variables	Number of subjects/observations (N), mean, standard deviation (SD), median and range.
Descriptive summary statistics for categorical variables	Frequency counts and percentages [n (%)]
Denominator for percentages	Number of subjects in the analysis population, unless stated otherwise in table shell(s)
Include "Missing" as category	Yes, when the number missing is greater than zero for at least one treatment group.
Display for 0 percentages	Blank
Display to one more decimal place than collected value	Mean Standard Error Mean Difference Median
Display to two more decimal places than collected value	Standard Deviation Confidence Interval
Limit of precision for displays	3 decimal places
Date Format	DDMMYYYY
Dictionary names and versions	The dictionary names and versions will be included in a footnote in all AE, medical history, prior and concomitant medication TFLs that present coded terms from the dictionaries.

Time to event or duration of event endpoints will be based on the actual date rather than Visit Day.

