7.6.4.2 Death

Number of subjects who died and the cause of death will be presented for each treatment group for the ITT population. The proportion of subjects who died along with 95% exact binomial CI (Clopper-Pearson) will be presented for each treatment group. Two-sided 95% CI will also be presented for the difference in percent of subjects who died between treatment groups with an approximate normal distribution. The Fisher's exact test will be used to compare the proportion of subjects who died. The two-sided p-value for the Fisher's exact test will be presented.

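### The normal-approximation 95% CI for the difference in admissions and deaths does not hold its stated coverage at about 50 per arm with few events; a score interval should replace it

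*SAP*

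**What the plan says.** For inpatient admission of more than 24 hours, SAP 7.6.4.1 specifies three outputs. Each arm gets a proportion with a Clopper-Pearson 95% CI. The contrast gets a two-sided 95% CI for the "difference in percent of subjects requiring hospital admission between treatment groups with an approximate normal distribution". The p-value is two-sided: "The Fisher's exact test will be used to compare the proportion of subjects requiring hospital admission". The endpoint "will be analyzed in the ITT population".

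SAP 7.6.4.2 repeats the scheme for death: "Two-sided 95% CI will also be presented for the difference in percent of subjects who died between treatment groups with an approximate normal distribution", and "The Fisher's exact test will be used to compare the proportion of subjects who died".

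The general rule for significance tests in SAP 7.1 is "Two-sided and use a 5% significance". The protocol synopsis (version 5.0) gives the arm sizes as "approximately 50 subjects assigned to brequinar 100 mg and 50 subjects to placebo", and SAP 2.4 allocates "in a 1:1 ratio at each site".

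Neither document states the standard error or any continuity correction for the difference interval, or an expected event rate for either endpoint. Protocol section 11 treats any testing as exploratory and descriptive.

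**The concern.** A normal-approximation interval for a difference in proportions needs a reasonable number of events in each arm. This trial enrols out-patients, about 50 per arm, so admissions may be few and deaths fewer. In that range the interval can be far too short, and with no events it reports a difference known without error.

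Reducing admissions and reducing mortality are both secondary objectives, and the results are meant to inform the design of later studies. A planner would take the plausible range of effect from this interval. If it covers the truth less often than stated, the next study inherits false precision. The interval will also sometimes exclude zero next to a p-value above 0.05, which makes the table harder to read.

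**Working it through.** **Inputs**
- Arm size: 50 v 50 (protocol synopsis). 49 v 51 was also tried, because the numbers are approximate.
- Nominal levels: 95% CI (SAP 7.6.4.1 and 7.6.4.2) and two-sided 5% for tests (SAP 7.1).
- Event rates: none are planned, so the rates below are assumptions. The 14% in Protocol 3.1 is background for everyone infected, not a control-arm rate for this population.
- There is no sample-size or power figure to reproduce. The figure to check is the stated 95%.

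**Interval checked.** With d the difference in observed proportions, the uncorrected Wald interval is d ± 1.96 × √[p₁(1−p₁)/50 + p₂(1−p₂)/50].

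**1. No events in either arm.** The standard error is 0, so the CI runs from 0 to 0. The SAP's own Clopper-Pearson interval for 0/50 has an upper limit of 1 − 0.025^(1/50) = 7.1%, so the same table would show per-arm uncertainty and none for the difference. At true rates of 2% v 1% this happens with probability 0.98⁵⁰ × 0.99⁵⁰ = 0.364 × 0.605 = 22%.

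**2. Coverage.** Binomial probabilities were summed over all 51 × 51 = 2,601 outcome tables:

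| Assumed true rates | Normal CI | Miettinen-Nurminen CI |
|---|---|---|
| 5% v 1% | 91% | 97% |
| 4% v 2% | 86% | 97% |
| 2% v 1% | 77% | above 99% |
| 14% v 7% | 94% | 95% |

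The shortfall is large at low rates and small at rates near 14%.

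**3. No true difference.** At common rates of 5%, 10%, 14% and 20% the normal CI excludes zero in 5.4%, 5.9%, 5.7% and 5.8% of trials, with a maximum of 6.1%. At a common rate of 2% it does so in 1.3%. Fisher rejects in 0.7%, 1.8%, 2.3% and 2.8% at the same four rates, with a maximum of 3.5% at exactly 50 v 50 and 4.6% at 49 v 51.

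**4. CI beside Fisher.** Take 5/50 on placebo and 0/50 on brequinar. Then d = 10% and SE = √(0.1 × 0.9/50) = 4.24%, so the CI is 10% ± 8.3%, or 1.7% to 18.3%. Fisher p = 2 × C(50,5)/C(100,5) = 2 × 2,118,760/75,287,520 = 0.056. For 4/50 v 0/50 the CI is 0.5% to 15.5% and p = 0.117. At 50 v 50 the CI excludes zero with Fisher p > 0.05 in 106 tables, and the reverse occurs in none. At 49 v 51 there are 64 such tables, again all in that direction.

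**5. How often they conflict.** This depends on unstated quantities. At 14% (placebo) v 7% (brequinar) the chance of a conflict is 11.5% with 50 v 50 and 11.1% with 49 on brequinar and 51 on placebo. It is 2.9% with 51 on brequinar and 49 on placebo. With 50 v 50 it is about 5% at 4% v 2% and about 1% at 2% v 1%.

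**6. The replacement.** At 0/50 v 0/50 the score limit solves d/(1−d) = 1.96² × (100/99)/50 = 0.0776, so d = 7.2% and the CI is −7.2% to 7.2%. Beside Fisher, 90 conflicting tables remain at 50 v 50.

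**The case against.** A reader might infer more than this: that the SAP sets up two rival 5% decisions for one contrast and leaves the author free to report whichever is favourable. The documents do not support that.
- Both sections name Fisher as the comparison. The CI is only presented in addition, and the 5% rule in SAP 7.1 is a rule for significance tests. Nothing says that a CI excluding zero counts as a positive result.
- Protocol section 11 makes all testing exploratory and descriptive, and no success rule attaches to these endpoints.
- Conflict rates of 11% or more at 14% v 7% arise where a true difference exists, so they mainly show that Fisher has less power. They also rest on a background rate and shift sharply with one subject more or less per arm.
- A Fisher p-value beside a large-sample interval is a common pairing. Dropping Fisher for an asymptotic score p-value would give up its guaranteed ceiling, which is a trade-off and not a correction.

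All of this stands against the decision-rule reading. None of it rescues the interval: if the CI is there as the estimate, its coverage is what matters, and the coverage fails at low event rates. A continuity correction would bring the CI close to Fisher at 50 v 50 (8 conflicting tables). At 49 v 51, however, it produces 30 tables where only Fisher is significant, and the SAP names no such correction.

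**Conclusion.** The point holds as a fault in the interval method. At about 50 per arm the planned CI for the difference can fall well short of 95% coverage (about 77% to 91% in the three low-rate scenarios), has zero width with no events, and excludes zero in up to 6.1% of null trials. Its occasional conflict with Fisher is real and one-directional in every arm split checked, but how frequent it is cannot be fixed from the documents.

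The result assumes an uncorrected Wald interval and low event rates. If admissions ran near 14% the coverage loss would be slight. For death, where rates of 1% to 2% are a fair assumption, the zero-width and coverage problems are the main issue and conflict with Fisher is rare (0.2% to 1.3% of null trials). Severity is modest because the endpoints are secondary and the testing is exploratory.

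**What to change.** In SAP 7.6.4.1 and 7.6.4.2, replace the normal-approximation interval with the Miettinen-Nurminen score 95% CI for brequinar minus placebo. Keep Clopper-Pearson for each arm and Fisher as the named comparison. Add one sentence stating that the CI is the estimate of the difference and is not a second significance test.

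The cost is a few lines of SAP text before database lock, using standard software. Some disagreement with Fisher remains: at 0/50 v 5/50 the score CI is −21.4% to −2.4%, still beside p=0.056. The score interval is also asymptotic, excluding zero in at most 5.7% of null trials at any common rate.

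A sponsor who wants the CI and p-value always to agree could use an exact unconditional score test with the CI obtained by inverting it. That needs slightly more computing, and replacing Fisher is optional.
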